4.1.2 Treatment period

Patients will be randomized to receive either BNT111 + cemiplimab combination therapy (Arm 1), BNT111 monotherapy (Arm 2) or cemiplimab monotherapy (Arm 3).

Treatments with BNT111 will be given once-weekly for the first 6 wks, followed by treatments once every 3 wks (±3 d). Cemiplimab will be given once every 3 wks (±3 d) throughout the trial.

The treatment period starts on Day 1 of Cycle 1 and continues for up to 24 months or until confirmed progression of disease, withdrawal of consent or unacceptable toxicity.

4.1.3 Add-on therapy for patients in Arm 2 or 3

Patients who experience disease progression under monotherapy may continue with addon therapy. Disease progression must be verified centrally. The eligibility of patients for the add-on therapy needs to be checked based on the inclusion criteria (Section 5.1.3) and exclusion criteria (Section 5.1.4). Patients need to re-consent for participation in the addon therapy.

Patients in Arm 2 (add-on of cemiplimab to BNT111): Cemiplimab will be given once every 3 wks (±3 d). BNT111 will be continued according to the planned schedule; a patient must have received a total of 6 weekly injections during the initial trial treatment and the add-on therapy before moving to a once every 3 wk schedule of injections.

Patients in Arm 3 (add-on of BNT111 to cemiplimab): BNT111 will be given once-weekly for the first 6 wks of add-on therapy, followed by treatments once every 3 wks (±3 d). Cemiplimab will continue to be given once every 3 wks (±3 d).

Page 45 of 133 Version: 7.0 Date: 09 FEB 2023

Treatments will continue up to a total treatment duration (monotherapy and add-on therapy) of 24 months.

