- Subgroup analyses in Section 7.3 (the subgroup "Best response to prior PD-1 + CTLA-4 combination inhibitor therapy (CR, PR, SD, PD)" and "Best response to prior PD-1 inhibitor therapy (CR, PR, SD, PD)" are excluded.
- Analyses of ORR described in Section 8.4.3.5 using BICR based on RECIST 1.1, in Section 8.4.2.6/Section 8.4.3.5 using investigator assessment based on RECIST 1.1, in Section 8.4.3.1/Section 8.4.3.5 using BICR/investigator assessment based on iRECIST.
- Analyses of DOR described in Section 8.4.2.3/Section 8.4.3.5 using BICR based on RECIST 1.1, in Section 8.4.2.6/Section 8.4.3.5 using investigator assessment based on RECIST 1.1, in Section 8.4.3.1/Section 8.4.3.5 using BICR/investigator assessment based on iRECIST.
- Analyses of DCR described in Section 8.4.2.2/Section 8.4.3.5 using BICR based on RECIST 1.1, in Section 8.4.2.6/Section 8.4.3.5 using investigator assessment based on RECIST 1.1, in Section 8.4.3.1/Section 8.4.3.5 using BICR/investigator assessment based on iRECIST.
- Exploratory analysis of duration of disease control (DDC) in Section 8.4.3.2 using BICR/Investigator assessment based on RECIST 1.1 and in Section 8.4.3.3 using BICR/Investigator assessment based on iRECIST.
- Analysis of TTR described in Section 8.4.2.4/Section 8.4.3.5 using BICR based on RECIST 1.1, in Section 8.4.2.6/Section 8.4.3.5 using investigator assessment based on RECIST 1.1, in Section 8.4.3.1/Section 8.4.3.5 using BICR/investigator assessment based on iRECIST.
- Analysis of PFS described in Section 8.4.2.5/Section 8.4.3.5 using BICR based on RECIST 1.1, in Section 8.4.2.6/Section 8.4.3.5 using investigator assessment based on RECIST 1.1 and in Section 8.4.3.1/Section 8.4.3.5 using BICR/investigator assessment based on iRECIST.
- Depth of response described in Section 8.4.3.2.
- Analysis of Overall survival in Section 8.4.2.7/8.4.3.6
- Analysis of Biomarker data Section 8.4.3.8.1

[figure not shown]

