7.3 Subgroups

Subgroup analyses will be performed for the primary endpoint (ORR based on BICR assessment using RECIST 1.1) and secondary endpoints DCR and PFS based on BICR assessment using RECIST 1.1. The analysis will be performed if the number of patients is substantial within each subgroup category. Substantial number of patients is defined as at least 10 patients in each of the subgroup categories for the BNT111 + cemiplimab treatment group. If there is a substantial number of patients for the BNT111 + cemiplimab treatment group then the analyses for the BNT111 and cemiplimab monotherapy treatment groups will be performed regardless of the number of patients in each subgroup category. The category "missing" will not be considered for the subgroup analysis.

The analysis will be performed for the BNT111 + cemiplimab, BNT111 and cemiplimab treatment groups using the CCI set.

The following subgroups, based on data collected before start of study treatment will be defined:

- Age group (Age < 70 years, Age ≥ 70 years)
- Sex (Male, Female)
- ECOG PS (ECOG PS 0, ECOG PS 1)
- BRAF mutation status (Mutated and Wild Type)
- Metastatic status ((M0, M1a, M1b), (M1c, M1d))
 - Number of prior therapy lines (1, 2 to 5). These subgroup categories will be identified from the prior cancer therapy CRF page.
- Anti-PD1 (programmed death protein 1) refractory/relapsed (Relapsed or refractory to prior PD-L1 treatment) (Yes, No)

These subgroup categories will be identified from the prior cancer therapy data by medical review. The categorization will be based on the last therapy line where anti-PD-1 or anti-PD-L1 was given. If the best response during the therapy is CR, PR or SD/non-PD (or disease status at the end of the therapy if best response is

Page 26 of 78 Version: Final v7.0 Date: 05Mar2024

missing) then the patient is considered as relapsed, otherwise it is considered as refractory.

If best response is "No evidence of disease" (or disease status at the end of the therapy if best response is missing) and if disease progression is within 3 months from end date of last line then it is considered refractory, otherwise it is relapsed (i.e. date of progression > last anti-PD-1/anti-PD-L1 end date + 3*30.4375). If the date of progression is partial and cannot be imputed then the patient will be excluded from the subgroup analysis.

Prior PD-1 inhibitor therapy (monotherapy, combination)

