These subgroup categories will be identified from the prior cancer therapy data by medical review.

Prior BRAF/MEK inhibitor therapy (Yes, No)

These subgroup categories will be identified from the prior cancer therapy data using ATC codes.

Prior chemotherapy (Yes, No)

Chemotherapy will be identified from the prior cancer therapy data using ATC codes.

Brain metastasis (Yes, No)

This will be selected using Target Lesion Assessment and Non-Target Lesion Assessment data where sub-location = Brain

Visceral metastasis (Yes, No)

This will be identified using Target Lesion Assessment and Non-Target Lesion Assessment data based on BICR assessment. If any of the site/any lesion is reported as having "visceral location" then visceral metastasis =yes.

- Time since the first diagnosis (>median time since the first diagnosis vs <=median
 time since the first diagnosis). The median time since the first diagnosis will be
 derived by treatment group. Time since the first diagnosis will be calculated as:
 Date of informed consent Date of first diagnosis + 1.
- Sum of target lesion at baseline (>median sum of target lesions at baseline vs <=median sum of target lesions at baseline). The sum of target lesion at baseline will be derived by treatment group.
- Presence of liver metastasis (Yes, No) (target or non-target)

This will be identified using Target Lesion Assessment and Non-Target Lesion Assessment data based on BICR assessment. If any of the site/any lesion is reported as having "Liver location" then liver metastasis = yes.

In addition, the below subgroups will also be considered:

Use of systemic antibiotics (Yes, No)

Page 27 of 78 Version: Final v7.0 Date: 05Mar2024

Use of systemic antibiotics will be determined from the concomitant medication data. Use of systemic antibiotics during the treatment period will be checked.

Use of systemic corticosteroids (Yes, No)

Use of systemic corticosteroids will be determined from the concomitant medication data. Use of systemic corticosteroids during the treatment period will be checked.

- Occurrence of irAE during the treatment and Safety follow-up period (Yes, No)
- Best response to prior PD-1 inhibitor therapy (CR, PR, SD, PD)

Note: In case of re-challenge (≥2 PD1i treatment received by patient prior to enrolment) "best response to PD1i" is defined as best response to last PD-1 inhibitor therapy.

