These subgroup categories will be identified from the prior cancer therapy data using ATC codes and best response to the therapy. Only patients who received PD-1 + CTLA-4 in combination will be included in this subgroup analysis:

 Best response to prior PD-1 + CTLA-4 combination inhibitor therapy (CR, PR, SD, PD)

The best response of the last PD-1 + CTLA-4 combination treatment taken before the first study trial treatment will be used.

Prior CTLA-4 inhibitor (yes, no)

These subgroup categories will be identified from the prior cancer therapy data and medical review.

Analysis detailed Sections 8.4.1, 8.4.2.1, 8.4.2.2 and 8.4.2.5 will be performed. All the subgroup analyses are exploratory, no adjustment for multiplicity will be performed. A p-value will not be presented.

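### SAP 7.3 groups ORR, DCR and PFS by irAE, steroid or antibiotic use over a window that lengthens with time to progression, so the irAE table can favour Yes when no link exists

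*SAP*

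**What the plan says.** SAP 7.3 opens its main list with "The following subgroups, based on data collected before start of study treatment will be defined". A second list follows, without that restriction, and includes three factors that arise on study:

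- irAE: "Occurrence of irAE during the treatment and Safety follow-up period (Yes, No")
- antibiotics: "Use of systemic antibiotics during the treatment period will be checked"
- corticosteroids: "Use of systemic corticosteroids during the treatment period will be checked"

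ORR, DCR and PFS by BICR under RECIST 1.1 are reported by each factor. PFS counts from randomization (SAP 8.4.2.5). Protocol 4.1.2 says that treatment "continues for up to 24 months or until confirmed progression of disease, withdrawal of consent or unacceptable toxicity". Protocol 6.3 lets it run past a first radiological progression, and safety follow-up adds 90 days after the last dose.

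The limits on these tables are a size rule ("Substantial number of patients is defined as at least 10 patients in each of the subgroup categories", applied to Arm 1), the statement that "All the subgroup analyses are exploratory, no adjustment for multiplicity will be performed", and the absence of p-values. SAP 5.2 puts the 7.3 subgroups among the IA2 outputs and leaves out only the two based on best response to prior therapy. Neither document gives a landmark, a fixed window, a time-dependent method or a caveat for the three on-study factors.

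**The concern.** Membership of the Yes group is settled after time zero, and the time available to enter it depends on the endpoint. A responder treated for a year has many months in which to record an irAE. A patient who progresses at the first scan has a few weeks of treatment plus the safety tail. Comparing the two groups from randomization credits Yes patients with the event-free time they needed in order to become Yes (immortal time). ORR and DCR are distorted the same way, because responders and patients with disease control have longer windows.

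At stake is interpretation. An irAE table that favours Yes by construction could be read, at IA2 or in the trial report, as evidence that irAEs mark benefit.

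A smaller related point concerns SAP 8.4.3.6. It reports OS from randomization in the Add-on Treatment set and in the set that excludes those patients. Entering the first requires surviving to confirmed progression and to the first add-on dose, so the two outputs do not describe comparable groups.

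**Working it through.** The plan gives no figure to reproduce, and the ORR design values are blacked out. The check asks what the tables show when there is no true link.

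**Inputs from the documents**
- 90 patients in Arm 1 (SAP Table 3.2); about 18 months of recruitment (Protocol 1.1).
- Treatment capped at 24 months; safety follow-up of 90 days = 2.96 months.
- The primary cut-off needs three post-baseline assessments. Scans fall at weeks 6, 12 and 21 (SAP Appendix 7), so it is taken as 21 weeks after the last patient.

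**Assumed inputs**
- ORR 25%. PFS is a 6-week lead-in (1.38 months) plus an exponential time with median 14 months in responders and 2.5 in others.
- Half of patients are treated 4-12 weeks past progression.
- irAE hazard independent of outcome: constant at 3-8% per month, or front-loaded at 15-20% per month for 3 months and then 1-2%. The documents make early events plausible: arthralgia and myalgia are expected flu-like symptoms (Protocol 6.8.4.1) and also listed irAE terms (Protocol Appendix 12.1).

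**Closed form: full follow-up, constant hazard h, no treatment past progression**

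With λ = ln 2 / median and c = 24 − 1.38 = 22.62:

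P(Yes) = 1 − exp(−h × (1.38 + 2.96)) × [λ/(λ+h) × (1 − exp(−(λ+h)c)) + exp(−(λ+h)c)]

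ORR in Yes = 0.25 × P(Yes|R) / [0.25 × P(Yes|R) + 0.75 × P(Yes|N)], where R is responder and N non-responder. ORR in No uses 1 − P(Yes).

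| h per month | P(Yes\|R) | P(Yes\|N) | ORR Yes | ORR No |
|---|---|---|---|---|
| 3% | 0.398 | 0.208 | 39% | 20% |
| 5% | 0.557 | 0.318 | 37% | 18% |
| 8% | 0.706 | 0.451 | 34% | 15% |

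**Simulation: 400,000 patients per scenario, with treatment past progression and staggered entry**

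| irAE pattern | ORR Yes vs No, full follow-up | ORR Yes vs No, primary cut-off |
|---|---|---|
| Constant 3-8% | 33-38% vs 15-20% | about 30-32% vs 21-23% |
| Front-loaded | 27-28% vs 22-23% | about 26% vs 24% |

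- Median PFS at the cut-off, constant hazard: 5.9-6.3 against 4.0-4.5 months.
- DCR, full follow-up, if half of non-responders progress at the first scan: about 74-78% against 52-58% (constant). Front-loaded, the gap is about 3-6 points.
- In simulated 90-patient arms at the cut-off, an ORR gap of at least 10 points favouring Yes appears in about 45% (constant) or 19-21% (front-loaded), against 14-18% for a random split. The 10-patient rule, applied to the whole-period grouping, almost never blocks the table.

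**Steroids and antibiotics**

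Assume 2-4% per month background use, plus extra use in the 6 weeks before progression among patients progressing within 6 months. Median PFS for Yes against No then runs from 9.0-9.7 vs 4.0-4.4 months (no extra use) to 4.0-4.6 vs 5.1-5.7 (extra use in 40%). The sign reverses.

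**Do the remedies work?**
- irAE events in days 1-35 only: ORR and DCR agree within 1 point.
- Week-12 landmark: residual median PFS is level at about 3.8 months. Retained: 90 × [0.25 × exp(−ln 2 × 1.38/14) + 0.75 × exp(−ln 2 × 1.38/2.5)] = 90 × [0.25 × 0.934 + 0.75 × 0.682] = about 67 patients.
- Time-dependent covariate: rate ratio 1.00.
- Expected Yes patients in the early window: 90 × (1 − exp(−h × 35/30.4375)) = 3 at 3% and 8 at 8%. Ten or more occur in 0-27% of arms. Front-loaded, 14-19 are expected and ten or more occur in 92-99%.
- Steroids and antibiotics at 10% extra use: the early window still gives ORR 19-22% vs 25%, and the landmark gives residual PFS 2.6-3.1 vs 3.9 months.

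**The case against.** The strongest reply is that these tables sit in a separate list to be considered only if numbers allow, are declared exploratory and print no p-value. That stands, and it keeps the point modest. It does not correct the printed rates, confidence intervals and Kaplan-Meier curves.

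The size rests wholly on assumed hazards. Under front-loading, the pattern with some support in the documents, the ORR gap at the cut-off is about 2 points. That also stands. No size has been worked out for IA2.

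The early window fails where it is most needed: with constant hazards the 10-patient rule would usually suppress the ORR and DCR tables. This is a real cost, but suppression is better than a distorted table. Day 35 is also only an example. It precedes the earliest scheduled scan counted from first dose (day 36, SAP 8.4.1), but some passages count scans from randomization and extra scans are allowed.

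A reader might infer that add-on events would be used to classify Arm 2 and 3 patients. The documents do not support that. SAP 8.1 limits the response and PFS analyses to data up to the day before the first add-on dose, and SAP 8.5.2 ends randomized-phase treatment-emergent AEs at add-on start. What is missing is a cross-reference in 7.3.

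A reader might also infer that the two OS outputs should be dropped. Both documents state an exploratory objective of OS for each single agent with or without add-on treatment, which these outputs serve, and no comparison is planned. Labelling is enough.

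**Conclusion.** The point holds for the three on-study factors in SAP 7.3. For irAE the direction of the artefact is predictable if irAE timing is unrelated to outcome: Yes looks better. Its size is uncertain. It is about 9 points of ORR and 2 months of median PFS at the primary cut-off under assumed constant hazards of 3-8% per month, and about 2 points of ORR if irAEs cluster early. It grows with follow-up.

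It would be tempting to say that the steroid and antibiotic tables are biased the same way. They are not necessarily: a longer window favours Yes, while use prompted by worsening disease favours No. Protocol 6.7.2 limits steroids above 5 mg prednisone largely to treating adverse events, so the second route is likelier for antibiotics.

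Nor does the point reach the primary ORR test or OS by arm as randomized. Neither uses these groups. The change is worth making because the rule is stated, can mislead and is cheap to replace.

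**What to change.** In SAP 7.3:

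1. **PFS:** replace whole-period grouping with a landmark (for example week 12, patients still progression-free, grouped by events up to then) or a time-dependent covariate.
2. **ORR and DCR:** group by events in a fixed early window from first dose, for example days 1-35, counted whether or not treatment has stopped. Apply the 10-patient rule afterwards. If it suppresses the table, do not print the whole-period version as a subgroup efficacy result.
3. **Arms 2 and 3:** state that the window for all three factors ends the day before the first add-on dose, with cross-references to SAP 8.1 and 8.5.2.
4. **Steroids and antibiotics:** label the tables descriptive, because none of these steps removes use prompted by worsening disease.

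In SAP 8.4.3.6, keep the OS outputs, but label the two from-randomization ones (Add-on Treatment set, and the set excluding it) as not comparable, because membership of the first requires surviving to add-on start.

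The cost is SAP wording and light programming. Under the assumptions above, the week-12 landmark drops about 25% of Arm 1 (67 of 90 kept), while a time-dependent analysis keeps everyone. The early window may leave too few Yes patients for an ORR or DCR table.

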8 STATISTICAL ANALYSES

8.1 General considerations

In general, the statistical analysis of efficacy will be performed by treatment group. Exploratory analysis will be performed for patients in the calibrator arms who went on to receive add-on treatment.

No formal statistical comparisons between treatment groups will be performed.

Continuous variables will be summarized by treatment group and total (as specified) using the following descriptive statistics: number of patients with non-missing data (n), mean, standard deviation (SD), median, minimum (min) and maximum (max).

Categorical variables will be summarized by treatment group and total (as specified), presenting absolute and relative frequencies (n and %) of patients in each category and the number of patients with missing data (missing' category will be presented if there is one or more missing value). The "(N=xx)" in the tables denotes the number of patients in the

Statistical Analysis Plan (SAP) BNT111-01

Page 28 of 78 Version: Final v7.0 Date: 05Mar2024

analysis set within each treatment group. For event-driven occurrence data (e.g., adverse event, concomitant medication, etc.) the percentages will be based on the number of patients in the analysis set (N). For reported visit data (e.g., gender, ECOG, etc.) the percentages will be based on the number of patients with non-missing values (n).

The rates of binary endpoints will be summarized by treatment group with absolute and relative frequencies (n and %) along with two-sided 95%-confidence intervals (CI) using an exact method. Exact confidence intervals for binomial proportions will be derived using the Clopper-Pearson method (Clopper, CJ and Pearson, ES⁵).

Time-to-event-endpoints will be analyzed using Kaplan-Meier methodology by treatment group and censored in accordance with the FDA Guidance: "Clinical Trial Endpoints for the Approval of Non-Cell Lung Cancer Drugs and Biologics² (Table 5.1). The main analysis will be done for each treatment group separately. Comparison of the treatment groups may be done as an exploratory analysis, with stratified and non-stratified analysis considered.

The overall number and type of events and the overall number and reason for censoring will be summarized (n, %) by treatment group. The median event/survival time (including two-sided 95%-confidence limits according to Brookmeyer and Crowley) and the first and third quartile will be presented. Survival rates (including two-sided 95% confidence intervals based on Greenwood's formula) as well as the number of patients with events, censored and under risk will be displayed for the selected time points.

The time-to-event analysis will be illustrated using Kaplan-Meier plots by treatment group and by treatment and randomization strata. Kaplan-Meier analysis and plots will be generated only if there are at least 3 patients in one treatment group.

Tumor response will be assessed by investigator as well as by blinded independent central review (BICR) of radiographic images and will be measured using RECIST 1.1 and iRECIST. The primary analysis will be based on BICR using RECIST 1.1, while investigators assessment and assessments based on iRECIST (BICR and Investigator) will be considered as secondary/exploratory analysis.

The iRECIST data will be imputed as per the programming guidelines. A separate programming guideline has been created for imputing iRECIST data for BICR assessment and investigator assessment using the RECIST 1.1 assessment.

The best overall response (required for the analysis in Sections 8.4.1, 8.4.2.1_8.4.2.4 and 8.4.2.6) for the BICR assessment and investigator assessment (using RECIST 1.1 and iRECIST) will be programmatically determined using the RECIST 1.1 and iRECIST guidelines. A separate programming guideline has been created for programming best overall response using RECIST 1.1 and iRECIST criteria. Confirmation of CR and PR is not required for the analysis, unless otherwise specified.

The primary and secondary efficacy analyses and analysis of efficacy data will be performed using the set. All data for patients in the set will be used for the analysis, even if the patient went on to receive add-on treatment, unless specified otherwise.

Statistical Analysis Plan (SAP) BNT111-01

Page 29 of 78 Version: Final v7.0 Date: 05Mar2024

The Safety set will be used for all safety analyses. The Add-on Treatment set will be used for analysis of both safety and efficacy data. Patients randomized to monotherapy (arm 2 and arm 3) who enter add-on treatment period are included in the analysis using both the mITT set, ITT set and the Add-on Treatment set, unless specified otherwise.

The following will occur for the analysis of ORR, DCR, DOR, TTR, PFS, OS, DEoR and EORTC endpoints and for the exploratory analysis of Duration of Disease Control (DDC):

- Tumor response endpoints ORR, DCR, DOR, DDC, TTR, DEoR and PFS: for the analysis using the set or set (sensitivity analysis for ORR (including DCR)), only the data until the day before first dose of add-on treatment will be used. For the analysis using the Add-on Treatment set, only the data from date of first dose of add-on treatment will be used.
- OS: for analysis using the set and Add-on Treatment set, all data would be used. For the exploratory analysis using the Add-on Treatment set (BNT111 + add-on cemiplimab and cemiplimab + add-on BNT111 treatment groups) the data from first day of add-on treatment would be used.
- For EORTC endpoints (Section 8.4.2.8) the summaries/analyzes will be performed as follows:
 - (i) While using set, data until the day before first dose of add-on treatment would be used.
 - (ii) In addition, a separate summary from first dose of add-on treatment to EOS, for the Add-on Treatment set.

All safety analyses will be based on the treatment actually received by the patient ('as treated'). All other analyses will be based on the treatment the patient was randomized to ('as randomized'), unless stated otherwise.

The following will occur for the analysis of safety data (apart from Adverse events)

- For the analysis of safety data using the Safety set, only data until the day before first dose of add-on treatment, if there is add-on treatment, or all data if there is no add-on treatment will be used.
- For the analysis of safety data using the Add-on Treatment set, only data from date of first dose of add-on treatment will be used.

The primary analysis of the trial will be performed based on all available data from a clinical data cut-off that will occur when all patients are randomized and response evaluable (i.e., having at least 3 post-baseline tumor assessments or discontinued before).

An analysis update will be performed when the last patient discontinued from the trial and once all patients have been randomized and have been followed-up for at least 24 months. An analysis update may be subsequently performed.

Statistical Analysis Plan (SAP) BNT111-01

Page 30 of 78 Version: Final v7.0 Date: 05Mar2024

Data up to and including the clinical cut-off date will be taken into account for the statistical analysis.

All analyses will be conducted using SAS® version 9.4 or higher.

Baseline is defined as last non-missing value prior to the first dose of trial treatment at C1D1. Assessments performed at C1D1 will be considered for baseline value, unless there is evidence the assessment was performed after trial treatment had been administered. For the add-on treatment if the baseline visit and AOC1D1 are on the same day, the assessment only needs to be taken once. In this case the AOC1D1 would be considered as the baseline value, unless there was evidence that the assessment was done after treatment had been administered.

To identify the baseline value, generally, if there are multiple assessments available for a particular day, the assessment that is closest to the day (and time if collected) of the first dose of the trial treatment (i.e., BNT111 or cemiplimab) will be used as the baseline value in the summary/analyses.

Multiple values at post-baseline visits: if there are multiple post-baseline assessments available within a visit/day, the first value and corresponding date/time will be considered.

Change from baseline will be calculated as follows:

Change from baseline = post-baseline assessment value – baseline assessment value.

If either the baseline or post-baseline assessment value is missing, the change from baseline is set to missing as well.

Duration (Other than "trial treatment duration" defined in Section 8.5.1) will be calculated as follows:

Duration = last observation date - first observation date + 1

For conversion of days to months or years the following rules will be applied:

- 1 month = 30.4375 days
- 1 year = 365.25 days

Trial Day and Treatment Day are defined as follows:

- Trial day:
 - If assessment date < randomization date then trial day = assessment date randomization date
 - If assessment date >= randomization date then trial day = assessment date randomization date + 1
- Treatment Day = treatment date date of first dose +1

That is, trial day 1 indicates the date of treatment initiation.

All trial data will be presented at the visit as collected in the eCRF. No windowing of data for the purposes of assigning to a visit will occur.

Statistical Analysis Plan (SAP) BNT111-01

Page 31 of 78 Version: Final v7.0 Date: 05Mar2024

Unscheduled assessments will be included in the analysis of efficacy endpoints for tumor response, time to event endpoints and shift from baseline to worst NCI-CTCAE Grade laboratory summary tables. All other unscheduled assessments will be listed only and not included in summaries/analysis.

If there is a difference between randomized and actual strata at randomization then the randomized strata will be used for analyses. A summary of randomized and actual strata at randomization will be presented. If there is a notable difference between the two summaries, then a sensitivity analysis for the primary endpoint will be considered.

Handling missing Data:

For the purposes of assigning treatment-emergent flag for AEs, partial or missing AE dates will be handled as follows:

- If the day of the month is missing, the onset day will be set to the first day of the
 month unless it is the same month and year as the first trial treatment. In this case,
 in order to conservatively report the event as treatment-emergent, the onset date will
 be assumed to be the date of the first trial treatment.
- If the onset day and month are both missing, the day and month will be assumed to be January 1, unless the event occurred in the same year as the first trial treatment.
 In this case, the event onset will be assumed to be the day and month of treatment in order to conservatively report the event as treatment-emergent.
- A completely missing onset date will be assumed to be the day of the first trial treatment.
- If an AE has a partial start date that is in the same month/year as the first dose of trial treatment, then the AE will be reported as treatment-emergent. If an AE has a missing start date, then the AE will be reported as treatment-emergent.

For the purposes of assigning treatment-emergent flag for irAEs, partial or missing irAE dates will be handled as follows:

- If the day of the month is missing, the onset day will be set to the first day of the
 month unless it is the same month and year as the first trial treatment of cemiplimab.
 In this case, in order to conservatively report the event as treatment-emergent, the
 onset date will be assumed to be the date of the first trial treatment of cemiplimab.
- If the onset day and month are both missing, the day and month will be assumed to be January 1, unless the event occurred in the same year as the first trial treatment of cemiplimab. In this case, the event onset will be assumed to be the day and month of treatment of cemiplimab in order to conservatively report the event as treatmentemergent.
- A completely missing onset date will be assumed to be the day of the first trial treatment of cemiplimab.

Statistical Analysis Plan (SAP) BNT111-01

Page 32 of 78 Version: Final v7.0 Date: 05Mar2024

 If an irAE has a partial start date that is in the same month/year as the first dose of trial treatment of cemiplimab, then the irAE will be reported as treatment—emergent.
 If an irAE has a missing start date, then the irAE will be reported as treatment—emergent.

For the purposes of assigning prior or concomitant flag for medications, partial or missing medication dates will be handled as follows:

- If end day is missing and month/year are non-missing, then day is the earliest of treatment end date (if month/year of treatment end date is same as the medication month/year) and the last day of the month.
- If end day/month are missing and year is non-missing, then day/month is the minimum of treatment end date (if year of treatment end date is same as the medication year) and the end of the year (31DECYYYY).
- If imputed end date is less than the start date, use the start date as the imputed end date.
- If the start date year is missing, the start date is set to one day prior to treatment start date
- If the start date year is less than the treatment start date year, then:
 - If the month is missing, the start date is assumed to be mid-year point (01JULYYYY).
 - Else if the month is not missing, the start date is assumed to be mid-month point (15MONYYYY).
- If the start date year value is greater than the treatment start date year, then:
 - If the month is missing, the start date is assumed to be the year start point (01JANYYYY).
 - Else if the month is not missing, the start date is assumed to be the month start point (01MONYYYY).
- If the start date year value is equal to the treatment start date year value:
 - If the month is missing or the month is equal to the treatment start date month, then the start date is assumed to be one day prior to the treatment start date.
 - Else if the month is less than the treatment start date month, the start date is assumed to the mid-month point (15MONYYYY).
 - Else if the month is greater than the treatment start date month, the start date is assumed to be the month start point (01MONYYYY).

If complete end date is available and the start date assumed from the steps above is greater than the end date, then the assumed start date should be set to the end date.

Partial anti-cancer therapy start dates will be handled as follows:

Statistical Analysis Plan (SAP) BNT111-01

Page 33 of 78 Version: Final v7.0 Date: 05Mar2024

- If the start of subsequent anti-cancer therapy date is missing, this will be imputed to the date of the EOT visit.
- Missing day, month/year present: If the month/year is the same as the month/year of EOT Visit date, then impute missing start dates with EOT Visit date. Otherwise, for dates corresponding to a start date, impute with the first day of the month.
- Missing month/day, year present: If the year is the same as the year of EOT Visit date, then impute missing start dates with EOT Visit date. Otherwise, for dates corresponding to a start date, impute with the first day of the year.
- If the EOT Visit date is missing, the date of last treatment will be used for imputation.

Partial date of progression for prior cancer therapies will be handled as follows, for the derivation of the time since the first diagnosis subgroup:

- Assign the day to the 15th of the month.
- If the month/year is missing, the date of progression will not be imputed.

Partial diagnosis dates will be handled as follows, for the derivation of the time since the first diagnosis subgroup:

- Assign the day to the 15th of the month.
- If the month is missing, the initial diagnosis date is assumed to be mid-year point (01JULYYYY).
- Else if the month is not missing, the initial diagnosis date is assumed to be mid-month point (15MONYYYY).

For analysis of pharmacodynamic data:

- The actual date collected will be used. If the date is not available, the value will be considered as missing.
- The actual time of sample collection will be used. If the time is not available, the value will, at the discretion of study pharmacodynamics analysist (in consultation with BioNTech), be considered as missing or imputed to be the nominal sampling time.

